**Table 1: Adrabetadex Dose and Infusion Volume** 

Dose Group a	Adrabetadex Volume	Volume of 0.9% NaCL	Total Infusion Volume
400 mg	2.0 mL	8 mL	10 mL
600 mg	3.0 mL	7 mL	10 mL
900 mg	4.5 mL	5.5 mL	10 mL

<sup>a Doses other than those provided in the examples above will be prepared in the same manner. NaCL = sodium chloride.

# 11.6. Measures of Treatment Compliance

Adrabetadex will be administered at the clinical site by a study clinician, and the amount of drug infused will be recorded in the dose preparation worksheet and maintained in the subject's medical record/source documents.

#### 12. STUDY PROCEDURES AND GUIDELINES

A schedule of assessments and procedures by time point is presented in Section 22.

Prior to conducting any protocol-related activities, written informed consent must be signed and dated by the subject or the subject's legal representative. If appropriate, assent must also be obtained prior to conducting any protocol-related activities.

Patients who have been screened, meet eligibility criteria, and have provided signed written informed consent will be enrolled. Baseline assessments will be completed at Screening, as described in Table 4.

#### 12.1. General Assessments

# 12.1.1. Demographic Information

Demographic information (eg, date of birth, gender, race, ethnicity) will be recorded at Screening.

#### **12.1.2. Medical History**

Relevant medical history, including history of NPC (eg, diagnosis date, prior treatments), other pertinent respiratory history, and information regarding underlying diseases, will be recorded at Screening.

# 12.2. Safety Assessments

#### 12.2.1. Prior and Concomitant Medications

Any medications used to treat NPC in the past (no time limit) and any other medications taken within 30 days of the Screening Visit will be collected at Screening. All concomitant medication and concurrent therapies will be documented at each study visit through Follow-up Visit 3. Dose, route, unit, frequency of administration, indication for administration, and dates of treatment will be captured using the appropriate CRF.

#### 12.2.2. Adverse Events

Information regarding occurrence of AEs will be captured throughout the study, beginning with the signing of informed consent and ending after procedures for Follow-up Visit 3. Information will be recorded on the appropriate CRFs. Definitions associated with AEs and the procedures for reporting them are presented in Section 14.1 and Section 14.2, respectively.

Any time a subject has a reported AE of special interest, ie, AE related to hearing impairment (National Cancer Institute Common Terminology Criteria for Adverse Events [CTCAE] grade 3 or higher), audiologic assessments need to be conducted. Audiologic assessments may also be conducted at the discretion of the investigator for hearing impairment AEs of CTCAE grade < 3(Section 12.2.6.1, Section 14.1.8).

## 12.2.3. Vital Signs

Blood pressure, pulse rate, respirations, and body temperature will be measured after a 5-minute rest in a supine position. At all visits when adrabetadex is administered, vital signs will be measured at two different times: 1) prior to LP and 2) after recovery from LP (as defined by institutional practices).

# 12.2.4. Physical Examination

At Screening, a complete physical examination will be performed by either the clinician or a designee who is a physician. Qualified staff (physician, nurse practitioner, registered nurse, or physician assistant) may complete an abbreviated physical examination at all other visits (every 6 months after first dose; first 6-month time point = Week 26). This abbreviated examination focuses on body systems with a change in health or new symptoms. New abnormal findings must be documented, captured as AEs, and followed by a physician or other qualified staff until the abnormality resolves or stabilizes, or until the subject discontinues from the study for reasons other than the AE. Weight will be collected at every visit.

# 12.2.5. Neurological Examination

A complete neurological examination will be performed by an experienced clinician at Screening and then every 12 months after first dose. An abbreviated neurological examination comprising assessments of eye movements, coordination, gait, and reflexes, will be conducted at every 6 months in between. A complete neurological examination will be conducted at End of Study/Early Termination. Clinically significant changes in the neurological examination will be identified by the investigator, captured as AEs (if not related to medical history, underlying disease or to another existing AE), and followed by a physician or other qualified staff until the abnormality resolves or stabilizes, or until the subject discontinues from the study for reasons other than the AE.

# 12.2.6. Audiologic Evaluation

Acoustic reflexes, pure tone audiometry (PTA), and auditory brainstem responses (ABRs) have been used to date to evaluate abnormalities that have been previously reported in NPC subjects (King 2014). As of 20 January 2021, ABRs will not be collected, as the potential risks with the procedure outweigh the potential benefit of the data.

#### 12.2.6.1. Audiologic Testing

Audiologic evaluations will be performed at the time points specified in Table 4.

Audiologic assessments will include:

- Evaluation of middle ear function (tympanometry).
- Air conduction PTA.
- Speech reception threshold.

• Bone conduction PTA (only at Screening and when a clinically significant change in hearing is observed in air conduction PTA).

A clinically significant change is defined as:

- ≥20 dB increase at any one test frequency relative to baseline measure.
- ≥10 dB increase at any two adjacent test frequencies relative to baseline measure.
- Loss of response at three consecutive test frequencies where responses were previously obtained (specifically the highest frequencies tested) on baseline measure.

#### 12.2.7. Clinical Laboratory Measurements

All clinical laboratory samples obtained will be sent to central or local laboratories as specified in the Laboratory Manual.

# **12.2.7.1.** Hematology

Blood will be obtained for a complete blood count (hemoglobin, hematocrit, red blood cell count, white blood cell count, white blood cell differential, and platelet count), and coagulation studies (PT and aPTT) at Screening and every 6 months after first dose (first 6-month time point = Week 26). If platelet count is below  $75 \times 10^9$ /L, the platelet count should be repeated and the clinician will need to make a clinical determination whether the subject can be dosed or should be discontinued from the study.

#### 12.2.7.2. Blood Chemistry Profile

Blood will be obtained for determination of serum sodium, potassium, chloride, bicarbonate, calcium, random glucose, blood urea nitrogen, creatinine, aspartate aminotransferase (AST), alanine aminotransferase (ALT), alkaline phosphatase, total bilirubin, direct bilirubin, albumin, and lactate dehydrogenase at Screening and every 6 months after first dose (first 6-month time point = Week 26).

#### **12.2.7.3.** Urinalysis

Urine will be obtained for determination of color, specific gravity, pH, protein, glucose, ketones, and blood. Urinalysis will be performed at Screening and every 6 months after first dose (first 6-month time point = Week 26).

# 12.2.7.4. Cerebrospinal Fluid for Routine Clinical Laboratory Tests

At the time of first treatment with adrabetadex in the study, a sample of CSF will be collected from treatment-naïve subjects just prior to adrabetadex infusion to be used for routine CSF analysis (red blood cell count, white blood cell count, white blood cell differential, glucose, and protein).

# 12.2.7.5. Pregnancy Test

For female subjects who are of childbearing potential, a serum pregnancy test will be obtained at Screening, and a urine pregnancy test will be obtained every 6 months after the first dose (first 6-month time point = Week 26).

# 12.2.8. Electrocardiogram

A 12-lead electrocardiogram (ECG) will be obtained and interpreted locally (at the study sites) for baseline screening/safety monitoring at the Screening visit.

# 12.3. Efficacy and Quality of Life Assessments

Efficacy assessments (NPC severity scale [NPC-SS], Clinician Clinical Global Impression of Change [CGIC]) and self-reported outcomes (EuroQol five-dimensional three-level version [EQ-5D-3L]) will not be collected.

#### 13. EVALUATIONS BY VISIT

See Table 4, Schedule of Assessments and Procedures.

For subjects continuing in the study after 21 June 2021, the investigator must assess whether the subject is benefiting from treatment with intrathecal adrabetadex. For those subjectss who appear to benefit from treatment, the investigator must review with them the risks associated with adrabetadex, including hearing loss, and the data from the randomized, controlled trial that demonstrated no significant differences between subjectss treated with adrabetadex and shamtreated subjectss on any efficacy measures. This discussion should be documented in the subject's medical record and only those subjects (or legally authorized representative) who have demonstrated an understanding of the risk/benefit of adrabetadex treatment should be permitted to continue in the study.

#### 14. ADVERSE EVENTS – DEFINITIONS AND REPORTING

# 14.1. **Definitions**

This section defines the different categories of AEs. The procedures for reporting AEs are described in Section 14.2.

#### 14.1.1. Adverse Event

An AE is defined as any untoward medical occurrence associated with the use of a drug in humans, whether or not considered drug related (Code of Federal Regulations [CFR] Title 21 Part 312.32).

An AE can therefore be any unfavorable and unintended sign (including an abnormal laboratory finding), symptom, or disease temporally associated with the use of the drug, without any judgment about causality (GCP definition).

#### 14.1.2. Suspected Adverse Reaction

A suspected adverse reaction is a subset of all AEs for which there is reasonable possibility (ie, evidence to suggest a causal relationship between the drug and the AE) that the drug caused the event (21 CFR 312.32).

#### 14.1.3. Serious Adverse Event

An AE or suspected adverse reaction is considered serious if, in the view of either the clinician or sponsor, it results in any of the following outcomes (21 CFR 312.32):

- Death
- A life-threatening AE
- Inpatient hospitalization or prolongation of existing hospitalization (hospitalizations for less than 24 hours with no admission are not considered "hospitalization")
- A persistent or significant incapacity or substantial disruption of the ability to conduct normal life functions
- A congenital anomaly/birth defect.

Other important medical events may also be considered SAEs when, based on appropriate medical judgment, they jeopardize the subject or require intervention to prevent one of the outcomes listed.

Procedures for reporting SAEs are described in Section 14.2.

## 14.1.4. Unexpected Adverse Event/Unexpected Suspected Adverse Reaction

An unexpected AE (or unexpected suspected adverse reaction) is any AE or suspected adverse reaction that is not listed in the Investigator's Brochure or is not listed at the specificity or severity that has been observed if an Investigator's Brochure is not required/available, or is not consistent with the risk information described in the general treatment plan (21 CFR 312.32). This also refers to AEs or suspected adverse reactions mentioned in the Investigator's Brochure

as occurring with a class of drugs or as anticipated from the pharmacological properties of the drug, but are not specifically mentioned as occurring with the investigational product.

#### 14.1.5. Serious and Unexpected Suspected Adverse Reaction

A serious and unexpected suspected adverse reaction (SUSAR) is any SAE related to investigational product, the specificity or severity of which is not consistent with those noted in the current protocol, Investigator's Brochure, or product labeling (no labeling exists for adrabetadex since it has not been approved for marketing). This also refers to AEs or suspected adverse reactions mentioned in the Investigator's Brochure as occurring with a class of drugs or as anticipated from the pharmacological properties of the drug, but are not specifically mentioned as occurring with the investigational product.

## 14.1.6. Adverse Event Severity

The CTCAE, Version 4.03 should be used to assess and grade AE severity, including laboratory abnormalities judged to be clinically significant. If the AE is not covered by the grading in the CTCAE, the general guidelines of the CTCAE grades should be applied (see Table 2) for grading the severity.

Table 2: Adverse Event Severity	Grading
--	---------

Severity (Toxicity Grade)	Description
Grade 1	Mild; asymptomatic or mild symptoms; clinical or diagnostic observations only; intervention not indicated.
Grade 2	Moderate; minimal, local or noninvasive intervention indicated; limiting age-appropriate instrument ADL*.
Grade 3	Severe or medically significant but not immediately life-threatening; hospitalization or prolongation of hospitalization indicated; disabling; limiting self-care ADL**.
Grade 4	Life-threatening consequences; urgent intervention indicated.
Grade 5	Death related to AE.

\*Instrumental ADL refers to preparing meals, shopping for groceries or clothes, using the telephone, managing money, etc.

#### 14.1.7. Adverse Event Relationship to Investigational Drug

The relationship of an AE to the investigational drug should be assessed using the following guidelines in Table 3.

\*\*Self-care ADL refers to bathing, dressing and undressing, feeding self, using the toilet, taking medications, and not bedridden.

ADL = activities of daily living; AE=adverse event.

Relationship to Drug	Comment
Definite	The AE follows a reasonable sequence from the time of study drug administration, follows a known response pattern of the study drug class, is confirmed by improvement on stopping the study drug, and/or the study drug definitely causes the event.
Probable	The AE follows a reasonable sequence from the time of study drug administration, follows a known response pattern of the study drug class, is confirmed by improvement on stopping the study drug, and/or is the most likely of all causes.
Possible	The AE follows a reasonable sequence from the time of study drug administration, but could also have been produced by the subject's clinical state or by other drugs administered to the subject.
Unrelated	Concurrent illness, concurrent medication, or other known cause is clearly responsible for the AE.

**Table 3:** AE Relationship to Investigational Drug

AE=adverse event.

# 14.1.8. Adverse Events of Special Interest – Clinically Significant Hearing Impairment

NPC and adrabetadex are both associated with hearing impairment. The severity and site of lesion of auditory damage may differ between adrabetadex- and NPC-induced hearing impairment; some lesion sites overlap, whereas some are more likely only in NPC. In addition, NPC hearing impairment progresses more slowly than drug-induced hearing impairment, which may occur abruptly within 24 hours of infusion at a given dose.

Any time a subject has a reported clinical AE of special interest, ie, AE of hearing impairment (CTCAE grade 3 or higher) audiologic assessments need to be conducted. Audiologic assessments may also be conducted at the discretion of the investigator for hearing impairment AEs of CTCAE grade < 3. Hearing impairment AE evaluation is described in Section 12.2.6.1.

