## **Summary of Safety Endpoints**

Treatment-emergent AEs (TEAEs) are defined as those AEs that are not present at Day 1 of study or represent the exacerbation of a pre-existing condition during the treatment period.

All AEs reported in this study will be coded using version 23.1 of the Medical Dictionary for Regulatory Activities (MedDRA®). Coding will be to lowest level terms. The verbatim text, the preferred term, and the primary system organ class will be listed.

Summaries of all TEAEs by treatment group will include:

- The number (n) and percentage (%) of subjects with at least 1 TEAE by system organ class and preferred term.
- TEAEs by severity, presented by system organ class and preferred term.
- TEAEs by relationship to treatment (related, not related), presented by system organ class and preferred term.

Deaths and other SAEs will be listed and summarized. TEAEs leading to permanent treatment discontinuation will be listed and summarized.

Laboratory test results will be summarized by baseline and change from baseline to each scheduled assessment time with descriptive statistics. Shift tables based on baseline normal/abnormal and other tabular and graphical methods may be used to present the results for laboratory tests of interest. Listings will be provided with flags indicating the out of laboratory range values.

Vital signs (body temperature, pulse rate, blood pressure, and respiration rate) will be summarized by baseline and change from baseline to each scheduled assessment time with descriptive statistics.

Changes in audiologic testing will be summarized by visit based on accumulated data at the time of analysis.

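### A hearing change that meets the protocol's own clinically significant criteria need not be recorded as an adverse event, and Section 18 plans no count of subjects who met them

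*Combined protocol and SAP*

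**What the plan says.** Section 12.2.6.1 (Audiologic Testing) lists three criteria for a clinically significant change: "≥20 dB increase at any one test frequency relative to baseline measure"; "≥10 dB increase at any two adjacent test frequencies relative to baseline measure"; and "Loss of response at three consecutive test frequencies where responses were previously obtained", the last aimed at the highest frequencies tested. The consequence given in that section is a further test: "Bone conduction PTA (only at Screening and when a clinically significant change in hearing is observed in air conduction PTA". The audiology footnotes to Tables 4 and 5 add monthly repeat audiograms after a change in hearing until it is stable.

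For other examinations the protocol sets a recording rule. Section 12.2.4 says of the physical examination: "New abnormal findings must be documented, captured as AEs". Section 12.2.5 has a similar rule for clinically significant neurological changes, with exceptions for medical history, underlying disease and events already recorded.

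Section 14.1.8 is headed with clinically significant hearing impairment as the event of special interest. It sets the level at grade 3: "AE of hearing impairment (CTCAE grade 3 or higher) audiologic assessments need to be conducted". Below that level: "Audiologic assessments may also be conducted at the discretion of the investigator for hearing impairment AEs of CTCAE grade < 3".

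Section 18 tabulates all TEAEs by system organ class and preferred term, by severity and by relationship. It lists no special-interest table. On hearing tests it says: "Changes in audiologic testing will be summarized by visit", using the data accumulated when the analysis is done.

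**The concern.** Hearing loss is the risk that the protocol names throughout, including in the discussion required before a subject may continue after 21 June 2021. TEAEs are the primary endpoint. If an audiogram can meet the protocol's own criteria without producing an event record, the incidence of hearing events depends partly on each site's recording habits, across as many as 30 sites.

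Event finding leans on conversation. Section 14.2.1 has the clinician ask the subject about events at each visit, and the schedule footnotes speak of subjective hearing events. Subjects may be as young as 4 years, and Section 5 describes progressive intellectual impairment. A measured shift that nobody reports is a plausible occurrence here.

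Information is lost as well as a count. Start date, grade and relationship to drug are recorded for adverse events. Section 14.1.8 says that drug-induced loss may be abrupt, within 24 hours of an infusion, while disease-related loss is slower. No section asks for a relationship assessment of a shift that was never entered as an event.

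**Working it through.** The study is descriptive and gives no figure on this point to reproduce. The check is to set the rules side by side and follow a hearing change to the tables.

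| Assessment | Threshold stated | Must be recorded as an AE? | Output in Section 18 |
|---|---|---|---|
| Physical examination | new abnormal finding | yes (12.2.4) | TEAE tables |
| Neurological examination | clinically significant change, judged by the investigator | yes, with exceptions (12.2.5) | TEAE tables |
| Laboratory tests | out of range | abnormal findings named in the AE definition (14.1.1) | change from baseline, flagged listings, optional shift tables |
| Audiology | three numeric criteria (12.2.6.1) | not stated | change by visit; criteria not used |

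**Paths to the tables**

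1. A recorded hearing event of grade 1 or 2 enters the TEAE incidence and severity tables, although it is not of special interest.
2. A recorded hearing event of grade 3 or higher enters the same tables. No separate table is planned.
3. An audiogram that meets 12.2.6.1 but is not recorded as an event enters no AE table. It contributes only to the by-visit audiology summary.

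Only path 3 loses anything from the primary endpoint. Its cause is the missing link from audiogram to event record.

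**Why the by-visit summary does not fill the gap.** Even if each visit's table showed how many subjects met the criteria, the number who ever met them would not follow. With a subjects at one visit, b at another and N in all, the number who met them at either visit lies between max(a, b) and min(a + b, N). Missing data are not imputed, so the subjects behind a and b may differ. Audiograms prompted by an event or repeated monthly need not fall on a tabulated visit.

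**Size.** Assume that the roughly 60 planned subjects are all in the denominator. Each subject with an unrecorded shift and no other hearing event lowers hearing-TEAE incidence by 1/60 = 1.7 percentage points. The total can range from zero, if sites record every such shift, up to the full proportion who met the criteria. The documents give neither end.

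**Timing.** From the protocol date, 23 June 2021, to the last permitted treatment date, 20 October 2021, is 7 + 31 + 31 + 30 + 20 = 119 days, or 17 weeks. Routine audiograms are 26 weeks apart with a window of 1 week either side, so at least 24 weeks apart. A recording rule applied only from now on would therefore reach at most one routine on-treatment audiogram per subject, plus the end-of-study and follow-up tests. A count derived from the stored audiograms covers the whole study.

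**The case against.** The strongest reply is that the plan already handles hearing. The AE definition in Section 14.1.1 covers any unfavorable sign and has no grade floor, so a site may record an audiometric shift. Recorded events below grade 3 are tabulated. Audiologic change is a named secondary endpoint. Section 12.2.6.1 concerns a change in a test and Section 14.1.8 a clinical event, so a shared adjective is not in itself an analysis error. All of this is correct. It shows that under-recording is possible rather than built in, and that the signal is not lost from the study. It does not supply the missing rule: permission to record differs from a requirement, and the protocol states the requirement for two other examinations.

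A reader might infer that the grade 3 level filters the AE summaries. It does not. It identifies the special-interest event and makes audiologic testing mandatory; Section 18 applies no grade filter and plans no special-interest count. Nor can one argue from Table 2 that a 20 dB shift must grade below 3. Table 2 applies only where CTCAE does not cover the event, and the CTCAE hearing criteria are not in the documents.

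A further objection is that a new recording rule this late would mix two ways of finding events. That is fair for the rule. It does not touch a count derived in the same way for every subject from audiograms already held.

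**Conclusion.** The point holds as a gap in recording and reporting. The plan defines a clinically significant hearing change, does not require it to be captured as an event, does not relate it to the other use of the same label, and does not count who met it. As written, the primary TEAE endpoint can under-report the drug's best-known toxicity.

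No figure can be put on the shortfall. A reader might try to size it from the 64% of subjects said to lose hearing through disease progression, or from the 14 of 14 participants with impairment in Study 13-CH-0001. Both say how often hearing loss occurs. Neither says what share meets the 12.2.6.1 criteria, how it would be graded, or how often sites would record it.

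The conclusion assumes that the three criteria are alternatives and that no manual outside these documents already requires such changes to be recorded. With no hypothesis testing and a negative benefit/risk conclusion already reached, this is a cheap improvement: it makes the final safety report easier to interpret and invalidates no planned analysis.

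**What to change.** **Section 18.** Add n (%) of subjects meeting each 12.2.6.1 criterion and any of them, at any time and by visit, derived for all subjects from existing audiograms, including unscheduled ones in the at-any-time count. Use as denominator the subjects with a usable baseline and at least one later audiogram, and state how many lack these; Table 4 foresees subjects who cannot give reliable pure tone results. Show the counts beside a table of hearing events across all grades, with the preferred terms listed beforehand. A time-to-first-change analysis is not advised, because routine audiograms are six months apart.

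**Sections 12.2.6.1 and 14.1.8.** State that a change meeting the criteria is captured and graded as an AE, as for the physical and neurological examinations. Say whether the underlying-disease exception of 12.2.5 applies. If it did, shifts could be left out on attribution, which Section 7.3 says cannot presently be determined. Reconcile the two clinically significant labels, for instance by using separate names for the audiometric change and the grade 3 or higher event.

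**If the AE rule is not applied retrospectively,** report events recorded before and after it separately.

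**Cost.** Protocol and analysis wording, a small amount of programming, and more low-grade AEs to record and report. No new tests are needed.
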